Following Randomization: After random assignment, participants will begin Tai Chi or Wellness treatment (12 weeks twice each week), half to each condition. Participants may be given a water bottle after attending Tai Chi or Wellness class. The water bottles have a logo that says "Whole Health Study" and display the Operation Desert Storm and Operation Desert Shield ribbon and the circular VA emblem. These water bottles may be mailed to participants with a thank you note from the study team. Participants engaged in the study at the 9-month follow-up assessment may also receive a 25th Anniversary Gulf War Challenge Coin. These coins may be mailed to participants with a thank you note from the study team. Participants in both conditions will receive assessments at baseline, 12 weeks (post-intervention), 24 weeks (approximately 3 months post-intervention) and 48 weeks (approximately 9 months post-intervention). (See Table 1 above.) Weekly measures will be collected by study staff via telephone and entered into a secure database remotely. Weekly measures may be mailed or e-mailed (via encrypted email messages) to participants so they can easily follow along with the weekly measure assessments. At the time of the collection of these weekly measures, feedback regarding preferences and areas for group improvement may be solicited from participants as

needed. This could include topics such as: best ways to maximize telehealth visibility and at-home Tai Chi setup; any feedback to relay to the instructor; preferences for the amount of sitting vs. standing for the class; preferences for the amount of group discussion vs. didactic instruction, etc. In addition, participants will be sent resources (e.g., VA Boston Whole Health handouts, IRB-approved virtual health resources) for continued engagement in health practices outside of group. This information will be recorded in an Excel spreadsheet that will use subject ID identifiers only and will be saved to a previously approved folder in the Drive: "[\\r04bhsnas61\resgroups\\$\PTSD\DATA\RESEARCH\TeleHealth](#) - [name]\Tai Chi Studies\Gulf War Study\Data". Information will be discussed at weekly lab meetings to help the study team improve the TeleHealth experience for group participants.

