Assessments. The primary outcome time point will be the 12-week assessment. (See Figure 1 above for study flow.) Assessments will consist of staff administered interviews and self-report assessment questionnaires. Participants will be remunerated for their time and inconvenience. Assessments are estimated to take 1 to 2 hours. Participants will be remunerated \$50 for the baseline assessment, up to \$50 for the post-treatment assessment, up to \$75 for the 3-month follow-up assessment, and up to \$100 for the 9-month (final) assessment. If participants are unable to come into VA Boston for any of the assessments, they will be given the opportunity to complete the assessment at home. Self-report measures will be mailed to participants and a self-addressed stamped envelope will be included with instructions for mailing the forms back to study staff. Assessment measures may also be emailed (via encrypted email messages) to participants as needed (e.g. if postal mailing delays are encountered, participants misplace forms, or if participants prefer email receipt). Participants will be reminded to not put their name on any forms or on the return address label to protect their confidentiality. Only participant ID numbers will be used on self-report measures. Study staff may call participants to check in on any questions participants may have about the assessments or clarify answers on paper and pencil assessment forms returned by participants if answers are ambiguous or have been skipped.

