Insomnia Severity Index (ISI) The ISI is a 7-item self-report measure that examines components associated with insomnia that may occur during the daytime and nighttime (Bastien, Vallières, & Morin, 2001).

PROMIS Self Efficacy for Managing Symptoms Short Form 8a (PROMIS Self Efficacy) The PROMIS Self Efficacy for Managing Symptoms is an 8-item self-report measure that examines elements of self-care (Gruber-Baldini, Velozo, Romero & Shulman, 2017). The PROMIS measures are freely available at <http://www.healthmeasures.net/explore-measurement-systems/promis>.

PROMIS Global Health Scale Short Form 8a (PROMIS Global Health) The PROMIS Global Health Scale is an 8-item self-report measure that examines physical function, fatigue, pain, emotional distress, and social health (Cella et al., 2010).

Chronic Pain Severity Scale (CPSS) The CPSS is a 22-item self-report measure that examines perceived self-efficacy to cope with components chronic pain such as pain management, physical function, and coping with symptoms (Anderson, Dowds, Pelletz, Thomas Edwards, & Peeters-Asdourian, 1995).

West Haven-Yale Multidimensional Pain Inventory (WHYMPI) The WHYMPI is 52-item self-report measure that examines experiences with chronic pain and engagement in everyday activities (Kerns, Turk & Rudy, 1985).

Physical Activity Recall (PAR) The PAR is a measure that will be administered by the study staff in an interview format. The PAR examines participants' physical activity over the past week and time spent sleeping (Sallis et al., 1985).

Mindfulness Attention Awareness Scale (MAAS) The MAAS is a 15-item self-report measure that assesses participants' openness towards, awareness of, and attention to the present. This scale can reveal information about one's self-regulation and well-being (Brown & Ryan, 2003).

Personal Health Inventory (PHI) The PHI is a 12-item self-report measure that assesses participants' relationship with each of the 8 dimensions of the VA Whole Health Circle (model that is frequently referred to throughout the course of the Wellness Intervention) including relationships, sleep, exercise, food and drink, personal development, spirituality, surroundings, and power of the mind. This scale will be administered to participants in the Wellness Intervention to measure potential growth across these 8 domains over the course of the study.

Measures of Satisfaction.

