Procedures for Randomization and Ensuring Blind Assessment. The Project Coordinator will use a random number generator from Random.org to create 10 tables of up to 16 integers limited to 1 (to denote Tai Chi) and 2 (to denote Wellness). After up to 16 participants are recruited and given consecutive participant numbers, study staff will release a randomization table to un-blinded staff and will assign condition in consecutive order. Un-blinded staff will record participant condition in a tracking excel file, and study staff will call participants to inform them of their condition assignment and schedule the group intervention sessions. Thus, all study staff will be blind to condition throughout the baseline assessment. When assessments are conducted remotely, the study will not maintain a blinded assessor. Blinding of staff is not necessary for remote assessments as participants will complete assessments on their own in their homes.

Statistical Plan and Data Analysis

SPSS, SAS, R, and RedCap will be used for data entry and/or analysis in this study.

Splitting the Study into Two Sub-Studies

The administrative halt on in-person research in 2020 required us to make several important changes to our research protocol. To adapt the Tai Chi intervention for telehealth, components that included sequential stepping and movement across the floor were removed and components done standing in one place were added. To adapt the Wellness intervention for telehealth, the method for reviewing SMART goals each week was altered; participants could not hand in their goal sheets for written feedback and instead group discussion time is devoted to goal setting. For the remote assessments, the physical function and neuropsychological measures could not be administered remotely in a valid and reliable manner and were removed from the assessment battery and a measure that addresses distress and functioning related to the pandemic was added. The protocols for the in-person and telehealth versions of the interventions differ enough that it would not be prudent to combine data from them. Thus, we propose to break up our clinical trial into two sub-studies: Sub-Study I (in-person) and Sub-Study II (telehealth).

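### The reason given for not blinding remote assessors does not hold for the PAR interview or the weekly telephone BPI, and holds only in part for mailed forms

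*Combined protocol and SAP*

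**What the plan says.** Procedures for Randomization and Ensuring Blind Assessment states that "When assessments are conducted remotely, the study will not maintain a blinded assessor", and gives one reason: "Blinding of staff is not necessary for remote assessments as participants will complete assessments on their own in their homes". The only staff blinding it promises ends before treatment starts: "Thus, all study staff will be blind to condition throughout the baseline assessment".

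Other sections describe staff taking part in remote data collection:

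- **Weekly measures** (Following Randomization): "Weekly measures will be collected by study staff via telephone and entered into a secure database remotely". A copy may be sent "to participants so they can easily follow along with the weekly measure assessments", so the paper or e-mailed form accompanies a call that staff run. The schedule table lists the BPI, the primary outcome measure, as weekly during treatment.
- **The same call** (Following Randomization): "At the time of the collection of these weekly measures, feedback regarding preferences and areas for group improvement may be solicited from participants as" needed. The example topics include the home set-up for Tai Chi and the balance of discussion against teaching. The answers are taken to weekly team meetings.
- **PAR** (Measures and Questionnaires): "The PAR is a measure that will be administered by the study staff in an interview format". The schedule table marks it under study staff at all four assessments.
- **Returned forms** (Assessments): staff may telephone to "clarify answers on paper and pencil assessment forms returned by participants if answers are ambiguous or have been skipped". The BPI is neither named nor exempted.

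**The concern.** The case for dropping blinding rests on staff having no hand in the answers. Where staff ask the question, hear the answer or settle an unclear one, that case fails, and a caller who knows the arm can influence what is recorded. Pain and recalled activity are subjective, so the risk is a real one.

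At stake are the credibility of the weekly pain trajectory, the between-arm comparison on the PAR, and any BPI item completed or altered on a clarification call. The 12-week BPI, which carries the primary comparison, is at stake only through clarification calls or through the way weekly scores enter the primary model.

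**Working it through.** The contradiction is textual. Arithmetic is needed only to see how far it reaches the primary endpoint.

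**Step 1. Compare the stated reason with each data stream.**

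| Stream | How collected | Does the reason hold? |
|---|---|---|
| PAR, post-treatment and both follow-ups | Staff interview | No |
| Weekly BPI | Staff telephone call, optional copy to follow | No |
| Mailed or e-mailed forms, including the 12-week BPI | Self-completed, then possible staff call | In part |
| Baseline PAR and BPI | Before randomization | Not at issue |

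**Step 2. Do weekly scores enter the primary model?** Data Analyses for Specific Aims puts all patient visits through week 12 into the GEE. It does not say whether a weekly call is a visit. The Human Subjects section uses visits for the four scheduled assessments. The question is open.

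**Step 3. If they do enter, how much of a shift in them reaches week 12?** Assume, for illustration only, that callers shift the weekly BPI by 0.3 SD between arms and leave the 12-week form untouched.

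*Time categorical (treatment-by-visit terms).* Each visit has its own treatment contrast. A constant shift in the weekly scores is absorbed by the weekly contrasts, so in principle none reaches week 12. Two simulations agree: one moved the week-12 contrast by 0.012 SD (0.012 / 0.3 = 4% of the shift). The other, with an assumed correlation of 0.6 and 15% random loss at week 12, moved it by 0.004 SD (simulation standard error 0.004).

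*Time linear.* The plan names visit as a main effect but writes the interaction as treatment-by-time, so linear time is not excluded. Take weekly scores at t = 1 to 12 and a self-completed score at an assumed t = 12.5, with exchangeable correlation. With balanced data the fitted contrast is then the ordinary least-squares line through the shifts:

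- mean t = (78 + 12.5) / 13 = 6.96
- mean shift = 0.3 × 12 / 13 = 0.277
- sum of squares of t = (650 + 156.25) − 13 × 6.9615² = 176.2
- slope = −0.3 × (12.5 − 6.96) / 176.2 = −0.0094
- fitted contrast at 12.5 = 0.277 − 0.0094 × 5.54 = 0.225 SD, or 75% of the shift

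That fraction depends on the correlation. With X holding an intercept and t, d the vector of shifts, and R having entries r^|ti − tj|, the estimate (X′R⁻¹X)⁻¹X′R⁻¹d gives 0.16 SD at r = 0.6 and 0.11 SD at r = 0.8. The plan specifies an unstructured correlation, so 75% is an illustration and not a prediction.

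**The case against.** The best defence is that the sentence concerns the scheduled assessment batteries, for which self-report forms are mailed home, and that weekly measures are a separate activity. The schedule table does class the BPI as self-report. A clarification call comes after the participant has filled in the form, and covers only unclear or missing answers. The plan also openly discloses that no blinded assessor is kept, and that the qualitative interviewer is unblinded. Much of this stands: clarification calls qualify the rationale rather than contradict it, and the weekly calls may lie outside what the sentence was meant to cover. It does not rescue the PAR, which is part of every scheduled battery.

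A second objection is that blinding callers achieves only so much. Participants know their arm, and a conversation about last week's activity may well reveal Tai Chi classes or home practice. This is true. Blinding staff limits interviewer influence and nothing more.

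A reader might infer two stronger things, and the documents support neither:

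- *That the primary test has an inflated false-positive rate.* This would need a shifted, telephone-collected score to supply the week-12 value, or weekly scores to enter a model that lets their shift through. Neither is stated. The size and direction of any caller effect would also be assumed. The investigators and coordinator may lead Wellness groups, so the direction need not favour Tai Chi.
- *That a blinded team already exists for these calls.* The plan mentions un-blinded staff, but promises blinding only through baseline. Study staff tell participants their assignment, and a research staff member attends every Tai Chi class.

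Nor does the text say that every caller knows the arm. It says only that no blinded assessor is maintained for remote assessments.

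**Conclusion.** The point holds in a limited form and should be acted on. The stated rationale is false for the PAR, does not apply to the weekly telephone BPI, and is incomplete for mailed forms. The data exposed are the weekly BPI series, the post-randomization PAR and clarified answers.

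For the self-completed 12-week BPI the consequence is small if time is categorical: 0.012 SD or less in simulation for an assumed 0.3 SD weekly shift. It could be material if weekly scores enter a model with linear time (0.11 to 0.22 SD under the correlations tried). The plan settles neither condition. All of these sizes rest on an assumed shift, because the documents give no basis for estimating the caller effect.

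**What to change.** - **Wording.** Replace the sentence in Procedures for Randomization and Ensuring Blind Assessment with one that limits the rationale to self-completed forms and acknowledges the staff-collected data.
- **Weekly BPI.** Have participants complete it on the form that may already be mailed or e-mailed, with the call as a reminder only.
- **Feedback.** Ask group-feedback questions separately from outcome collection.
- **PAR and clarification calls after randomization.** Where existing staff allow, give them to people who are not told the arm and are not present when feedback is discussed. Otherwise report these data as collected unblinded.
- **Primary value.** Name the self-completed 12-week BPI as the week-12 value. State whether weekly scores enter the GEE and, if so, that time is categorical in the interaction.

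The cost is protocol wording and some reassignment of calls, possibly with a separate contact for feedback. Whether present staffing is enough cannot be judged from the documents. Some weekly forms will come back late or not at all. If weekly collection has already begun, the change would mix modes within the series, so the mode of each score should be recorded. None of this removes participants' own expectation bias.

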Specific Aim 2: Evaluate whether the Tai Chi intervention improves fatigue, cognition, quality of life, and physical functioning in GW Veterans with GWVI, as compared to the Wellness intervention. We hypothesize that participants randomized to the Tai Chi intervention will evidence more improvement in fatigue, cognitive functioning, quality of life, and physical functioning than those randomized to the Wellness intervention and will maintain changes over a 9-month follow-up period.

The proposed trial, informed by our prior investigations, with a robust study design and strong research team, will produce valuable results that can have a direct and immediate impact on healthcare practices for GWVI. If proven as an effective treatment for the symptoms of GWVI, this non-pharmaceutical treatment could easily be implemented in VA facilities and Veterans could be taught how to continue to practice independently within their own homes. Providing GW Veterans even moderate relief from chronic and debilitating symptoms of GWVI could have a profound impact on improving their overall sense of wellbeing and quality of life, the ultimate measure of treatment efficacy.

Background and Significance

Following their deployment to the 1991 Gulf War (GW), many Veterans reported a constellation of unexplained health symptoms including widespread chronic musculoskeletal pain, fatigue, headaches, memory and attention difficulties, gastrointestinal complaints, and mood and sleep problems. The symptom complex persists for many Veterans despite the passage of time. Indeed, it is estimated that at least 25 percent of GW Veterans (170,000 Veterans) have a persistent form of chronic multisymptom illness (CMI) (Kang et al., 2009; RAC, 2008; IOM, 2010). Chronic musculoskeletal pain and fatigue are some of the most debilitating symptoms of CMI. To date, no treatments have been shown to substantially improve pain and fatigue without significant undesirable side effects, including exacerbating concurrent cognitive symptoms. Identifying effective, safe, and tolerable treatments for the symptoms of Gulf War Veterans' Illness (GWVI) is therefore of paramount importance.

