Post-treatment and follow-up assessments will also include a qualitative interview that may be audio-recorded (if the participant agrees to be audio-recorded) to gather information about participants' experiences in and following the group interventions. Given the nature of this instrument, the interviewer will not be blinded to the intervention. If participant interviews are conducted remotely and recorded by staff via telephone, the audio recorder will be stored in a locked box at the interviewer's home. Study staff will bring the recorder in the locked box to the VA at regular intervals to upload the content to a secure location and then delete the contents from the recorder. As an alternative to using an audio recorder, VA WebEx and Teams software may be used to record these sessions. The remuneration is increased for the latter assessments in order to provide incentive to complete these follow-up assessments and to compensate participants for ongoing commitment to the research project. Participants will be remunerated \$10 for use of video devices and inconvenience for each intervention session they attend, for a total of up to \$240. On occasion, in-person assessments may need to be cancelled with little warning due to staff illness or other unforeseen events. In these cases, participants who cannot be reached prior to the assessment time and who arrive at the study site for the assessments may be compensated \$25 for their time and inconvenience.

Measures and Questionnaires.

Primary Outcome Measure

The Brief Pain Inventory – Short Form (BPI). The BPI is a self-report measure that examines how pain may interfere with functioning across different areas of life such as general activity, mood, work, walking activity, relationships, enjoyment of life, and sleep across 9 items

(Cleeland & Ryan 1994; Cleeland, 2009). Other questions pertain to pain relief, intensity, quality, and the patient's perception of the cause of the pain.

Secondary Outcome Measures. The following measures will be used to provide a comprehensive description of the sample of Veterans and scores on these measures may be used as covariates in planned analyses.

Demographics. Participants will be asked to report their age, years of education, gender, sex, race, ethnicity, relationship/marital status, employment status, current living situation, number and age of children (if any).

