Splitting the study into two parts has important implications for data analysis and the interpretation of our results. In March 2020, we had randomized 53 participants (27 to Tai Chi and 26 to Wellness) in Sub-Study I and 43 (81%) completed post-treatment assessments. This number falls substantially short of the original target of enrolling 120 Gulf War veterans and the administrative halt on research precluded us from continuing to enroll to approach the enrollment target. As a result, the power to detect differences between the two intervention groups is low, an unfortunate consequence of low enrollment due to a restricted sample of Boston-area GW Veterans and the premature termination of the study. Analysis of data from Sub-Study I would include examination of the rich qualitative interview and satisfaction data we have collected as well as within-group changes on outcome measures. We expect that this will yield important results that will guide future studies. [name], the Scientific Program Officer for Gulf War studies, has approved this change to the analytic plan for our study.

Participant Attrition and Missing Data

Based on results from previous studies conducted by the PI with medical populations and with Tai Chi and physical activity interventions, it is anticipated that a high rate of participants will complete all assessments. A high rate of completion is also anticipated since participants will be compensated for their assessments and will have established rapport with study personnel. Participants who drop out of treatment will be encouraged to remain in the study and to

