complete all assessments. In order to provide incentive to complete the follow-up assessments and to compensate participants for ongoing commitment to the research project, participants will receive additional compensation for the later assessments. Although rigorous attempts will be made to keep participants in the study and to gather complete data at each of the scheduled assessments, we conservatively anticipate up to 20% attrition and other incomplete data at the 12-week assessment due to factors outside our control (e.g. participant unwillingness, time constraints). In addition to planning for dropouts a priori by recruiting a larger sample, we plan to conduct intent-to-treat analyses (see below) to protect against potential bias that may occur when individuals drop out of the study due to their level of disability and their response to treatment and by using imputation methods for missing data as described below.

Data and Power Analysis for Sub-Study II

With 80 participants in the telehealth study (40 in each condition), assuming that 15% would not complete the post-treatment assessment, we would have sufficient (.80) power to show a medium-large between group effect (0.69). Importantly, we would also have .80 power to detect a medium (0.5) within-group effect.

Data Analyses for Specific Aims

The goal of the primary analysis is to determine whether participants in the Tai Chi Condition show more advantageous change in Brief Pain Inventory scores from baseline to 12-week assessment than those in the Wellness Condition. The analysis will follow an intent-to-treat approach (all randomized patients will be included in the analysis). The primary analysis will compare groups on the change from baseline Brief Pain Inventory to 12-week using generalized estimating equation (GEE) analysis of covariance adjusting for baseline score. The GEE analysis model will incorporate change from baseline to all patient visits through 12-week into the analysis, and will include main effects of treatment, visit, and the baseline score, and a treatment-by-time interaction effect. From this model, an assessment of the treatment difference on mean change from baseline to 12 weeks will be carried out on the robust estimates using a two-sided 0.05 level of significance. An unstructured correlation structure will be assumed as the within-patient correlation between time points.

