The primary analysis will be based on all available data. However, as supportive analyses, missing Brief Pain Inventory scores will be imputed at each visit in a monotone manner via multiple imputation linear regression approach and the above analysis will be repeated on the imputed data. Specifically, the imputation model will include important covariates such as age, gender, and baseline Brief Pain Inventory score. A total of 10 imputed datasets will be generated, and the above GEE analysis will be carried out on each imputed dataset; the Week 12 score results will be combined across the 10 datasets using the standard techniques for multiply imputed data sets in order to yield on overall Week 12 on the imputed data.

Similar analyses will be used for secondary endpoints. We anticipate that the distribution of the pain scale and scores on secondary outcome measures will be skewed, and that log transformed scores will be used in the analysis.

Human Subjects Research

a. Human Subjects Involvement and Characteristics

The participant population is to be comprised of up to 140 male and female Gulf War Veterans. These individuals will be recruited on a volunteer basis. Only individuals who provide written informed consent may participate. A participant may withdraw his/her consent at any time and without prejudice. A clear and detailed explanation will precede all procedures.

Informed consent will be obtained by the study PI or by another IRB-approved study staff member prior to the initiation of any study procedures. Informed consent will be reviewed with the participant at the beginning of this scheduled appointment, prior to initiating the assessment.

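### Sub-Study I was randomised, but the only outcome analysis the plan names for it is within-group change; an exploratory between-arm estimate should be added

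*Combined protocol and SAP*

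**What the plan says.** The section on splitting the study divides the trial into Sub-Study I (in-person) and Sub-Study II (telehealth), because the two versions "differ enough that it would not be prudent to combine data from them". It also records that the "physical function and neuropsychological measures could not be administered remotely in a valid and reliable manner and were removed from the assessment battery" when assessment became remote.

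For Sub-Study I it reports 53 randomised (27 Tai Chi, 26 Wellness) and 43 (81%) with post-treatment assessments. It calls the power to compare the arms low and says the analysis would include "examination of the rich qualitative interview and satisfaction data we have collected as well as within-group changes on outcome measures". It adds that the programme officer for Gulf War studies "has approved this change to the analytic plan for our study".

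The power statement that follows is headed for Sub-Study II. The next heading, on data analyses for the specific aims, sets out a between-arm GEE model for the Brief Pain Inventory (BPI) in which "all randomized patients will be included in the analysis". It then says "Similar analyses will be used for secondary endpoints". Neither sentence names a sub-study.

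Specific Aim 2 is worded as a between-arm hypothesis: Tai Chi participants "will evidence more improvement in fatigue, cognitive functioning, quality of life, and physical functioning than those randomized to the Wellness intervention".

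**The concern.** Randomisation gives Sub-Study I a concurrent comparison group. Change within one arm mixes any effect of Tai Chi with the passage of time, the attention of a twice-weekly group, and regression to the mean in people selected for chronic symptoms. The Wellness arm exists to remove those influences, and it does so only if the arms are compared.

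Most is at stake for the physical-function and neuropsychological tests. They are no longer given in Sub-Study II and the data will not be combined, so no later analysis of telehealth data can supply a randomised comparison of them. If the Sub-Study I report keeps to what the plan names, that comparison may never be published, although the data needed for it would already be in hand.

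**Working it through.** **Inputs from the plan.** Sub-Study I: 27 and 26 randomised, 43 with post-treatment data. Sub-Study II: 40 per arm, 15% without a post-treatment assessment, 0.80 power for a between-group effect of 0.69 and for a within-group effect of 0.5. Two-sided level 0.05. Cohorts of about 12, half to each condition, so classes of about 6.

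**Inputs assumed.** The arm split of the 43 is not given; I take 22/21. The extremes are 17/26 and 27/16. The baseline-to-12-week correlation r is taken as 0.5, with 0.7 as an alternative. The intraclass correlation (ICC) within a class is taken as 0.01 to 0.10.

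**1. The plan's own figures.** Completers per arm in Sub-Study II: 40 × 0.85 = 34. The two-sample t test with 34 per arm at 0.69 has power 0.800. The paired t test with n = 34 at 0.5 has power 0.808. Both agree with the plan. For Sub-Study I, 43/53 = 81%, also as stated; 10 of 53 (19%) have no post-treatment data.

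**2. Unadjusted between-arm precision, in outcome SD.** Half-width = t(0.975, 41) × √(1/n1 + 1/n2).

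- 22/21: 2.020 × 0.3051 = 0.62
- 17/26: 2.020 × 0.3119 = 0.63
- 27/16: 2.020 × 0.3155 = 0.64

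For comparison, Sub-Study II as planned (34/34) gives 1.997 × √(2/34) = 0.48. The Sub-Study I interval is 0.616/0.484 = 1.27 times as wide.

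**3. With baseline adjustment.** Half-width = t(0.975, 40) × √(1/n1 + 1/n2) × √(1 − r²). For 22/21 this is 2.021 × 0.3051 × √(1 − r²):

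- r = 0.5: 0.617 × 0.866 = 0.53
- r = 0.7: 0.617 × 0.714 = 0.44

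**4. With class clustering, unadjusted.** Multiply 0.616 by √(1 + (m − 1) × ICC). Classes of about 6 with 81% assessed leave about 5, so m is between 5 and 6; take 5.5.

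- ICC 0.01: 0.616 × √1.045 = 0.63
- ICC 0.10: 0.616 × √1.45 = 0.74 (0.73 at m = 5, 0.75 at m = 6)

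This makes no allowance for the small number of classes, which would widen the interval further.

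**5. Power.** With 22/21 the difference detectable with 0.80 power is 0.88 SD unadjusted, and power at 0.69 is 0.60. Describing between-arm power as low is therefore fair. Within-arm testing is weak too: at a within-group effect of 0.5, paired power is 0.61 (n = 22) and 0.59 (n = 21), against the 0.80 the plan cites for Sub-Study II.

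**6. Where the removed tests can be compared.** They are not given in Sub-Study II and the sub-studies are not pooled. That leaves Sub-Study I, where within-group change is the only outcome analysis named.

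**The case against.** The strongest reply is that the choice is deliberate and disclosed. The plan gives the shortfall, says why enrolment stopped, reports that the change was approved, and presents the results as guidance for future studies. It makes no efficacy claim, and the 0.88 SD detectable difference supports its judgement on power. All of that stands. It justifies not making the comparison confirmatory. It does not justify leaving out an estimate with its interval.

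A reader might infer more than the documents support:

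- *That the plan rules out a between-arm comparison in Sub-Study I.* It does not. The sentence lists what the analysis would include, which is not exhaustive.
- *That the between-arm model clearly leaves Sub-Study I out.* Its position after the Sub-Study II power heading suggests so, but the inclusion of all randomised patients could be read the other way. One sentence would settle it.
- *That Aim 2's cognition and physical-functioning hypotheses have no outcome at all in Sub-Study II.* The retained questionnaires are headed as secondary outcome measures, even though the text beneath says they "will be used to provide a comprehensive description of the sample of Veterans and scores on these measures may be used as covariates", and similar analyses are promised for secondary endpoints. PROMIS Global Health includes physical function and the MFI-20 includes mental fatigue. What is missing is an explicit mapping.
- *That significance in one arm alone will be presented as a Tai Chi effect.* No such test or claim is planned.

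**Conclusion.** The point holds as a cheap improvement, not as an error. No stated figure is wrong, and the telehealth comparison on the BPI is unaffected. For Sub-Study I the plan names a weaker analysis than its design allows and does not commit to the randomised comparison, which for the removed tests is available nowhere else.

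The cost of low power is an interval of about ±0.62 SD unadjusted (0.62 to 0.64 across possible splits), about ±0.53 SD with baseline adjustment at r = 0.5, and roughly ±0.63 to ±0.74 SD unadjusted once clustering is allowed for. That is wide but reportable.

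These widths rest on the assumed completer split, baseline correlation and class ICC. That the removed tests were collected in Sub-Study I is implied by their removal from the battery; the current measures section does not describe them.

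**What to change.** In the section on splitting the study, after the sentence on Sub-Study I analyses, add wording such as:

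*For Sub-Study I, the baseline-adjusted difference between arms at 12 weeks, with 95% confidence interval, will be reported as exploratory for the BPI and for the physical-function and neuropsychological tests as collected. All randomised participants with available data will be analysed in the arm assigned. Clustering by class will be taken into account or stated as a limitation. No multiplicity-adjusted or efficacy claim will be made. Within-group changes are descriptive and are not evidence of efficacy.*

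The cost is this wording and one model per outcome on data already collected, with no new participants or visits. The downside is a set of wide, exploratory intervals.

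Two clarifications are optional: state that the between-arm analysis under the specific-aims heading applies to Sub-Study II, and name the measure and sub-study that address each Aim 2 domain.
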